#### 6 SAMPLE SIZE DETERMINATION

Sample size calculations were generated under the assumptions that the three study arms are 1) mesh augmented sacral colpopexy, 2) transvaginal mesh repair, and 3) native tissue repair for vault prolapse. Further assumption was that the study would have an overall Type I error rate of 0.05, that a randomization ratio of 1:1:1 is preferred for feasibility reasons, and that the Type I error (alpha) would be distributed among the 3 following three hypotheses related to the 3 treatment arms in a way that optimizes sample size and at the same time is scientifically defensible:

• H1: transvaginal mesh is noninferior to mesh augmented sacral colpopexy [spend alpha of 0.03 using a one-sided noninferiority test]

• H2: mesh augmented sacral colpopexy is superior to native tissue repair [spend alpha of 0.01 using a two-sided test of superiority]

• H3: transvaginal mesh repair is superior to native tissue repair [spend alpha of 0.01 using a twosided test of superiority]

The sample size estimates also assume that the primary analyses for each of the three hypothesis tests will be based on a survival analysis model with a 2-year recruitment period and a 3-year follow-up period after the last participant is randomized and that loss to follow-up on each arm will be no more than 5% per year, that the 2-year success rates for mesh-augmented sacral colpopexy and transvaginal mesh repair will be 80% and that the 2-year success rate for native tissue will be 60%. These 2-year success rates represent hazards of 0.1116 and 0.2554, respectively, under the assumption that the failures follow an exponential survival model. The non-inferiority margin was selected to show that transvaginal mesh success rate at 2 years is no worse than a 15% difference from sacral colpopexy, or 65%. This success rate represents a hazard of 0.2154 and the noninferiority margin corresponds to a hazard ratio of 1.93.

Under the assumptions outlined above, the hypothesis test that drives the sample size is the test on noninferiority of transvaginal mesh to mesh-augmented sacrocolpopexy. A sample size of 121 participants per arm will provide **85%** power to demonstrate noninferiority under the assumptions outlined above. Assuming that 121 participants will also be randomized and treated to native tissue repair, the overall sample size of 363 participants will provide greater than **93%** power to demonstrate that each of the mesh augmented arms is superior to native tissue repair under the assumptions outlined above.

After April 18, 2019, the study was closed to new surgeries of transvaginal mesh. The remaining 18 consented or randomized patients were randomized to receive either sacral colpopexy or native tissue repair in a 1:1 ratio. This modification is expected to have minimal to no impact on the planned statistical power, given that the recruitment period had been extended from 2 years to 36 months (thereby increasing power), and the final sample size of the TVM group will be approximately 95% of the planned size, while the other two study arms are expected to meet or even slightly exceed the planned sample size.

# 7 STATISTICAL / ANALYTICAL ISSUES

#### 7.1 General Statistical Methods

All statistical methods will be based on the International Conference on Harmonisation (ICH) E9 document "Statistical Principles for Clinical Trials" unless otherwise requested by journal. All statistical computations will be performed, and data summaries will be created using SAS 9.4 or higher. If additional statistical packages are required, these will be identified in the presentation of results.

In summary tables of continuous or ordinal numeric variables, the mean, median, 25th and 75th percentiles (Interquartile range IQR), confidence interval (CI), standard deviation (SD) and standard error (SE) will be presented to one more decimal place than the original data.

In summary tables of categorical variables, counts and percentages will be used. The denominator for each percentage will be the number of subjects within the population treatment group unless otherwise specified.

All hypothesis testing will be carried out at the 5% (2-sided) significance level and confidence intervals will be 95% unless otherwise specified.

P-values will be rounded to three decimal places. P-values less than 0.001 will be reported as < 0.001 and greater than 0.999 will be reported as 0.999.

## 7.2 Adjustments for Covariates

Indicator variables for the study stratification factors of site (see site pooling in multisite studies, below) and age category (<65 and  $\geq$ 65) will be included as covariates in most efficacy analyses performed for this study.

## 7.3 Handling of Dropouts and Missing Data

Standard procedures will be used to ensure that data are as complete and accurate as possible. The study was designed to obtain as much follow-up data as possible on all randomized subjects. In analyses, a full accounting will be made for all data items. Generally, missing data will initially be treated as randomly missing (either missing at random (MAR) or missing completely at random (MCAR) as appropriate for the analytic approach) with no data imputation. Sensitivity analyses addressing the impact of missing data will be specifically specified.

**Impact of COVID 19** Some of the follow-up period of this study coincided with the COVID pandemic (March 2020 – July 2022). At varying times across sites during the pandemic, patients were unable or unwilling to attend in-person visits, or clinic site personnel were unable to conduct inpatient visits. Accommodations were made allowing for remote phone contact visits rather than inperson visits. All such visits were noted as a COVID-related protocol violation. As a result, there are more study visits missed than ordinarily expected in pre-pandemic, and also a percentage of study visits done remotely in which the subjective assessments of the primary outcome were recorded, but the anatomical POP\_Q exam of prolapse was not able to be performed. An effort was made by all sites to have participants complete a final POP-Q exam prior to study completion whenever possible. Assessments of the impact of missingness from the COVID pandemic on the primary outcome and sensitivity analyses are specified in applicable sections below.

#### 7.4 Interim Analyses and Data Monitoring

Given the unique nature of a three-arm randomized surgical trial, the Steering Committee initially considered the development of stopping rules for this protocol. The working group also considered the performance of a pilot study, but the disadvantage of enrollment of eligible patients that would not be used in the analysis was believed to offer minimal advantages compared to the development of an ancillary recruitment plan for slow recruitment versus futility/stopping rules for minimal recruitment. After careful consideration, the Steering Committee elected not to have formal stopping rules but to allow the DSMB and Steering Committee to monitor recruitment on a regular basis (similar to other PFDN studies). Thus, enrollment will initially be assessed 6 months after initiating the study. Based on prior PFDN studies, a goal of 20% of total enrollment will be set. If this goal is not obtained, additional non-network sites will be considered from a pool of sites pre-approved prior to this time.

The working group also considered the possibility of having one or more formal interim analyses that would provide for early stopping for a demonstrated efficacy benefit but rejected that option for two reasons. First, the study is designed to enroll only 121 participants per treatment arm, and the group was concerned that stopping the study with fewer participants than 121 per arm, even with relatively small p-values, might limit the impact of any findings on clinical practice because of the small sample sizes. Second, the hypothesis tests among the 3 arms, with a combination of superiority and non-inferiority hypotheses, will be complicated to explain to the clinical community if all 3 arms enroll to study completion. Stopping one of the arms early and testing two of the 3 hypotheses with a less than full sample and taking the other two arms to completion would complicate the explanation of the study even further. Given the small likelihood of stopping a study early for 2 of the 3 hypotheses, the complications of the approach appear to outweigh any potential benefits.

#### 7.5 Masked Data Review

A masked data review is planned prior to the data lock once all study participants reach the 36-month visit. Details of the results from the masked review will be documented in a SAP addendum once the review is complete. Specific items to be addressed in the masked data review are:

- Reason for study withdrawal and missed visits (adverse event, death, patient moved, lack of efficacy, etc. to determine whether the event was likely to be missing at random or informatively missing).
- Characterization of individual failures (by time and reason for failure) to ascertain failure time for the primary outcome and failure across time span for secondary analyses related to changing status of anatomical prolapse failure and bulge symptoms.
- Review of deviations (excluding missed/incomplete visits/assessments)
- Visit window outliers
  - All baseline data will be used regardless of time of collection so long as the data were collected prior to treatment initiation. If more than one assessment of an outcome is reported within a visit window, the earliest assessment will be used. If no assessments are available for a visit (e.g., assessments were completed but none within study window), then an out of window assessment will be used for that visit so long as the out of window assessment does not also fall into a window for a different study visit. Rules for classifying visit membership for out of window assessments will be further determined as part of a masked data.
- Classification of complications and adverse events based on indicator variable definitions from the SAP. The summary will include a count and percentage for each of the

complications listed in manuscript table shells as well as a table that shows the percentage of individuals having different numbers of complications. The summary will also include the distribution of Dindo scores, and the listing of complications that generated the Dindo scores.

- After completion of manual review and prior to final database lock, queries will be issued as follows:
  - Change all exposure or erosion complications to explicitly state "for/from prolapse surgery" or "for/from sling" (case insensitive) as appropriate.
  - Assure that all exposure or erosions reported on the AE log were also recorded on a complications table as indicated in the preceding bullet.

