#### **9.3** Efficacy Variables **Timepoint(s)** Variable Type Definition CRF Source **Primary Efficacy Outcome** 6 months through 60 Time to surgical CRF-13, Continuous Among subjects who experience a surgical failure (see months CRF-12, definition below) starting at the 6 month post-operative failure CRFvisit through their last attended ASPIRE visit, the time to surgical failure is defined as the number of months (i.e. 14/37 months as intended by the visit schedule) from the surgical intervention to first post-operative visit with surgical failure. Surgical failure is defined at each attended post-operative visit if any ONE of the following criteria is met: Retreatment failure is defined as retreatment for \_ prolapse via additional surgery or pessary as reported on coordinator follow-up CRF-13 Anatomic failure is defined as any prolapse beyond the hymen (i.e. POPQ points Ba, Bp, or C > 0.0 cm) as reported on the evaluator (blinded) follow-up CRF-12 during POPQ examination Symptomatic failure is defined as experiencing bothersome vaginal bulge symptoms as reported on CRF-14/37. Bothersome vaginal bulge symptoms are defined as a positive response to Question 3 Do you usually have a bulge or something falling out that you can see or feel in your vaginal area? AND any degree

of bother greater than "Not at all" (i.e. "Somewhat",
"Moderately", or "Quite a bit")
Participants not meeting the criteria for surgical failure at the attended post-operative visit will be considered not a surgical failure, regardless of missingness of the 3 components of the surgical outcome (i.e. retreatment failure, anatomic failure, and symptomatic failure).
The time to surgical failure will be missing for all participants who are considered not a surgical failure at each of the attended post-operative visits 6 months through their last attended ASPIRE visit scheduled in 6- month intervals up to 60 months.
Note that since ASPIRE followed participants until the last participant completed their 36 month visit, ASPIRE study completers have a varying amount of follow-up time from 36 to 60 months.
For survival analysis, participants with no failure by their last attended study visit are censored, and with follow-up duration equal to the number of months (i.e. months as intended by the visit schedule) corresponding to the last attended visit.

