# **9.4.1** Primary Efficacy Outcome

The primary efficacy outcome is the time to surgical failure and is evaluated using all the data collected through the last operated subject's 3-year visit (primary endpoint). Since enrollment spanned 3 years, the duration of follow-up for some subjects included in the primary analysis is 5 years (60 months). Specifically, among subjects who experience a surgical failure, time to surgical failure is defined as the number of months (i.e. 6, 12, 18, 24, 30, 36, 42, 48, 54, or 60 months as intended by the 6-month interval visit schedule through a maximum of 5 years) from surgical intervention to first surgical failure at any post-operative visit 6 months through a maximum of 5 years after surgery.

Though surgical failure status is recorded at the 6-weeks post-operative visit, this data is not analyzed as these measures are collected too close to the date of surgical intervention. Instead, all subjects who attended the 6-week post-operative visit (i.e. 1.5 months) will be considered as not surgical failures at this visit. Subjects without a surgical failure at the end of follow-up are censored at their last attended visit.

A participant will be considered a surgical failure at the post-surgical visit if any ONE of the following criteria is met:

- Retreatment failure: retreatment for prolapse (surgery or pessary)
- Anatomic failure: prolapse beyond the hymen
- Symptomatic failure: bothersome vaginal bulge symptoms

Based on the definition of the primary outcome, the primary analytic approach will utilize a survival model to evaluate differences in time to surgical failure between the surgical arms.

Supporting numbers for survival analysis will be presented, including the number censored in each surgical arm in each period (from model-based approach described below) as well as the median, 25th, and 75th percentile for follow-up time in months for each surgical arm.

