# 9.4.2 Primary Efficacy Analysis: Model-Based Survival Analysis

This model-based approach will serve as the primary analytic method for testing the comparative efficacy of the three strategies for uterovaginal prolapse as it can control for study design and potentially confounding variables. To appropriately account for the interval censored and right censored nature of the primary outcome data, and potential violation of the proportional hazards assumption across the entire follow-up time, while controlling for study design and potentially confounding variables in assessing intervention effects, a piecewise exponential (PWE) survival model will be employed. The PWE survival model is a model in which the time scale is divided into *K* periods and the underlying hazard function, h(t), is assumed to be constant within each period such that  $h(t) = \lambda_k \exp(\beta \mathbf{X})$ , where  $\lambda_k$  is the hazard function for period *k*, and **X** is a matrix of explanatory

variables with vector  $\beta$  coefficients (Breslow 1974). This piecewise approach effectively eliminates the need to specify the distribution of the hazard function and satisfies the proportional hazards assumption if the underlying hazard is constant within each period.

Among subjects who experience a surgical failure, the time to surgical failure (primary outcome) will be interval censored (i.e. lower bound, upper bound where both bounds are non-missing and lower bound < upper bound). Subjects who do not experience a surgical failure will be right censored (i.e. non-missing lower bound and missing upper bound) at their last attended visit. Specifically, the censoring interval for implementation in interval censored analysis will be defined as follows:

- lower bound = number of months (i.e. months as intended the by visit schedule) from the surgical intervention to the *last attended visit where the subject was considered to be not a surgical failure* across all post-operative visits starting at the 6 month visit. As such, subjects who were surgical failures at the 6-month post-operative visit will have a lower bound of 1.5 months corresponding to the 6-week post-operative visit. Based on this definition, the lower bound for the primary endpoint of 3 to a maximum of 5 years can take any of the following values 1.5, 6, 12, 18, 24, 30, 36, 42, 48, 54, or 60 months.

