- upper bound = number of months (i.e. months as intended by the visit schedule) from the surgical intervention to *first post-operative visit with surgical failure* across all attended post-operative visits starting at the 6 month visit. As such, subjects who do not experience a surgical failure through the endpoint, will have a missing upper bound and will be right censored at their lower bound. Based on this definition, the upper bound for the primary endpoint of 3 to a maximum of 5 years can take any of the following values 6, 12, 18, 24, 30, 36, 42, 48, 54, or 60 months.

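### The earliest-in-window rule in SAP 7.5 lets the primary time-to-first-failure outcome ignore a failure documented later in the same visit window

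*SAP*

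**What the plan says.** Under visit-window outliers, SAP 7.5 sets the rule for repeat assessments: "If more than one assessment of an outcome is reported within a visit window, the earliest assessment will be used". Visits after week 6 are six-monthly with a window of six weeks either side (SAP 7.8), so each window spans 12 weeks.

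SAP 9.4.1 defines the event as the "first surgical failure at any post-operative visit 6 months through a maximum of 5 years after surgery". The three components come from separate forms (SAP 9.3): POP-Q on CRF-12, retreatment on CRF-13 and bulge symptoms on CRF-14/37. A woman who meets no criterion at an attended visit "will be considered not a surgical failure, regardless of missingness of the 3 components of the surgical outcome". SAP 9.3 adds that this calculation is not altered for remote COVID visits.

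SAP 7.3 explains that remote visits recorded the subjective components without a POP-Q, and that "An effort was made by all sites to have participants complete a final POP-Q exam prior to study completion whenever possible".

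Dating is set in 9.3 and 9.4.2, not in 7.5. The upper bound is the "number of months (i.e. months as intended by the visit schedule) from the surgical intervention to" the first failing visit. The lower bound is likewise the "number of months (i.e. months as intended the by visit schedule) from the surgical intervention" to the last attended failure-free visit. Women without failure are censored "with follow-up duration equal to the number of months (i.e. months as intended by the visit schedule) corresponding to the last attended visit".

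**The concern.** A rule that keeps the first of several assessments suits a by-visit table of means. It does not suit a time-to-first-failure endpoint, where the later assessment may be the one that records the event. The resulting error runs in one direction: failures can be removed or delayed, never added.

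This outcome decides all four primary hypotheses. For the non-inferiority test, fewer events in both arms means less power. The trial also expects failures to come and go: the E-ASPIRe addendum says so, and the descriptive cross-sectional analysis in SAP 9.4.3 treats anatomic and symptomatic failure as transient. A failure ignored in one window is therefore not certain to be seen again.

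**Working it through.** **1. What happens to a later positive result in the same window.** Take a negative POP-Q at week 24 and a positive one at week 30, both in the 6-month window (weeks 20 to 32). Under 7.5 the 6-month visit is a non-failure.

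- *Failure persists and she attends at 12 months.* The recorded interval is (6, 12] months, about weeks 26 to 52. The data show (24, 30] weeks. The lower bound sits at a visit whose window already contains an observed failure, and the interval runs 52 − 30 = 22 weeks past the date of that observation.
- *Failure resolves.* It is never counted.
- *The window is her last.* She is right-censored as failure-free. E-ASPIRe data are outside this SAP (4.4.2).

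**2. Catch-up POP-Q after a remote contact in the same window.** The result depends on a word the SAP leaves undefined.

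| Reading of *outcome* | First assessment in window | Catch-up POP-Q |
|---|---|---|
| Each component | No POP-Q was done remotely, so the catch-up is the first POP-Q | Used |
| Composite | The remote visit already counts as non-failure with POP-Q missing (9.3) | Ignored |

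**3. Scheduled-month dating.** Assume that visits fall evenly across the ±6 weeks. A visit late by x weeks places failures from those x weeks before they happened. A visit early by x weeks places the last x weeks' failures after they happened. The mean absolute offset is 6/2 = 3 weeks in each 26-week cycle, so about 3/26 = 11.5% of failures have intervals that exclude the true time. The first interval has a fixed lower bound, and a simulation that allows for this gives about 10%. Early and late errors offset each other: in the same simulation, the hazard fitted to scheduled times divided by that fitted to actual times is 1.00.

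**4. Power for H1.** Inputs from SAP Section 6: 2-year success 80%, so h = −ln(0.80)/2 = 0.1116 per year; margin 1.93; one-sided alpha 0.03; 121 per arm; 2 years' accrual; 3 years' further follow-up; 5% loss per year, so d = −ln(0.95) = 0.0513 and t = h + d = 0.1629.

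P(event) = (h/t) × [1 − (e^(−3t) − e^(−5t))/(2t)] = 0.326

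This is 39.5 events per mesh arm and 242 × 0.326 = 79.0 in the two arms together. With E events, power = Φ(½ √E × ln 1.93 − 1.881). At E = 79.0 this is Φ(2.922 − 1.881) = 85.1%, which reproduces the plan's 85%.

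The share of failures lost is an assumption, taken as equal in both arms:

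| Failures lost | Events | Power |
|---|---|---|
| 0% | 79.0 | 85.1% |
| 1% | 78.2 | 84.8% |
| 2% | 77.4 | 84.4% |
| 5% | 75.0 | 83.3% |
| 10% | 71.1 | 81.4% |

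**The case against.** Much can be said for the plan.

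- **Natural reading.** The components sit on separate forms, so reading the rule by component is natural, and then no catch-up POP-Q is lost. A reader might infer that the rule discards the examinations sites went back to obtain; the text supports that only on the composite reading. This stands, but the SAP does not choose between the readings, and its treatment of missing components keeps the composite one open.
- **Recapture.** A persisting failure is counted at the next attended visit. It would be wrong to treat every later in-window failure as lost. This also stands.
- **Masked review.** SAP 7.5 lists "Characterization of individual failures (by time and reason for failure) to ascertain failure time for the primary outcome" among the review items, and 7.8 leaves out-of-window handling to that review. An examination at week 42, between the 6-month and 12-month windows, is therefore not fixed in advance and may be filed at 12 months, where the interval contains it. But neither provision overrides the explicit in-window rule. The addendum meant to record the review is not among the documents, so it may have settled some of this.
- **Arm balance.** A reader might infer a bias toward non-inferiority. The documents do not show one: the rule ignores arm and POP-Q examiners are masked. Participants are unmasked after surgery, and those randomized to TVM were told of the FDA statement, so attendance could differ by arm. No passage says that it did.
- **Unscheduled visits.** Counting every positive result lets extra attendance add events. This is a real cost of the fix.

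**Conclusion.** The concern holds in a limited form. As written, SAP 7.5 can set aside a documented failure when an earlier assessment of the same outcome in that window was negative. That conflicts with the definition of the primary endpoint. The failure is lost only if it resolves or falls in the last window; otherwise it is counted late. Whether a catch-up POP-Q is affected depends on a definition the SAP does not give.

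The size is probably modest. With equal loss in the two mesh arms, power for H1 stays between 84.8% and 81.4% for losses of 1% to 10%. That range is assumed, because the documents give neither the number of windows with two assessments nor the number of later positives among them. Scheduled-month dating is a separate and smaller matter: it misplaces roughly one failure in ten under evenly spread visit times, with little effect on the hazard ratio if timing is balanced.

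**What to change.** For the primary outcome only:

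1. State that all components assessed in a window are combined, and that a positive result on any component at any assessment in the window counts as failure.
2. Set the bounds from actual visit dates. The upper bound is the first positive assessment. The lower bound is the last earlier assessment at which the failing component was actually assessed and negative. For anatomic failure that means the last negative POP-Q, not a remote contact, because a contact without a POP-Q cannot show that she was free of prolapse. If two components turn positive together, use the earlier of their two lower bounds.
3. Keep the earliest-assessment rule and scheduled months for the by-visit secondary tables.
4. Report the number of double-assessed windows by arm, and how many had a later positive result, so that readers can judge the influence of extra visits.

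The cost is a short SAP edit and a change to the derivation program; the interval-censored model accepts actual times. SAP Section 12 already reports event counts by arm, so a change made now should be presented as a post-hoc sensitivity analysis beside the planned one.
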